5.4. Safety Assessment

The reporting of safety data is descriptive, and will include all subjects in the Safety population. The variables for safety endpoints are AEs. AEs will be summarized based on their frequency and their severity. All AEs will be coded using Medical Dictionary for Regulatory Activities (MedDRA) and summarized by treatment group. Data will be summarized using preferred term and primary system organ class.

If a subject experiences multiple events that map to a single preferred term, the greatest severity and strongest Investigator assessment of relation to study drug will be assigned to the preferred term for the appropriate summaries. Should an event have a missing severity or relationship, it will be classified as having the highest severity and/or strongest relationship to study drug.

Summaries of treatment-emergent AEs will include any AEs reported beginning with the first dose of study drug on Day 1. The occurrence of treatment-emergent adverse events will be summarized by treatment group using preferred terms, system organ classifications, and severity. Separate summaries of treatment-emergent serious adverse events, treatment-emergent adverse events related to study drug, and events leading to the discontinuation of study drug will be generated. All adverse events reported will be listed for individual subjects showing both verbatim and preferred terms.

Concomitant medications will be coded using the World Health Organization (WHO) drug dictionary. These data will be summarized by treatment group. Previous and concomitant medications will be presented in a data listing.

5.4.1. Adverse Events

Analysis of adverse events as safety variables will be based on all adverse event (AE) capture measuring severity and frequency utilizing MedDRA terminology for consistency. AEs will be mapped to a MedDRA-preferred term and system organ classification. If a subject experiences multiple events that map to a single preferred term, the greatest severity and strongest Investigator assessment of relation to study drug will be assigned to the preferred term for the appropriate summaries. Should an event have a missing severity or relationship, it will be classified as having the highest severity and/or strongest relationship to study drug.

Summaries of treatment-emergent AEs will include any AEs reported beginning with the first dose of study drug on Day 1. The occurrence of treatment-emergent adverse events will be summarized by treatment group using preferred terms, system organ classifications, and severity. Separate summaries of treatment-emergent serious adverse events (SAEs), treatment-emergent adverse events related to study drug, and events leading to the discontinuation of study drug will be generated.

5.4.2. Vital Signs

Vital signs will be collected at the Screening visit; on the Baseline, and at Visit 5 (or upon subject discontinuation). Vital signs will include body temperature (oral), heart rate and blood pressure (systolic and diastolic). Any abnormal characteristics will be evaluated by the Investigator based on their clinical significance. Abnormal vital signs will be considered AEs if they require therapeutic medical intervention, and/or if the Investigator considers them to be AEs due to the clinical judgement.

5.4.3. Previous and Concomitant Medications

All medications (both prescription and nonprescription, and including vitamins, herbals, topical, inhaled, and intranasal) taken within 30 days prior to the start of the Study Drug and through the final study visit will be recorded on the appropriate eCRF (using their generic and brand names, if known) with the corresponding indication, start and stop dates. At each study visit, subjects will be asked whether they have started or discontinued any medication since their previous study visit. This includes single use or PRN (as needed) medication use.

Previous treatment of head lice must be recorded irrespective of the term it was given. Corresponding condition shall be captured in the subject's Medical History.

6. CHANGES IN THE PLANNED ANALYSES

No deviations in the conduct of the study or the planned analysis are anticipated. Should any deviations from the analyses specified in the authorized statistical analysis plan arise, such deviations will be documented in the final clinical study report.

7. PROGRAMMING CONVENTIONS

Statistical programs will be developed using SAS® version 9.4 or higher. Programs will be documented, produced, and validated. Additionally, the following conventions should be incorporated:

• Page orientation, margins, and fonts: Summary tables, listings, and figures will appear in landscape orientation. There should be a minimum of a 1.25" boundary on the upper (bound) edge, and a minimum of a 1.0" boundary on the remaining three edges. Output should be printed in Courier New with a point size of at least 8. Titles may be printed using a larger font (e.g., Arial point size 10).

- Identification of analysis population: Every summary table and figure should clearly specify the analysis population being summarized. Listings will be prepared for all subjects.
- Group headers: In the summary tables, the group headers will identify the treatment group and the within-group sample size for the indicated analysis population. Of note, the header's sample size does not necessarily equal the number of subjects summarized within any given summary module; some subjects in the analysis population may have missing values and, thus, may not be summarized.
- Suppression of percentages corresponding to null categories: When count data are presented as category frequencies and corresponding percentages, the percent should be suppressed when the count is zero in order to draw attention to the non-zero counts.
- Presentation of sample sizes: Summary modules should indicate, in one way or another, the number of subjects contributing to the summary statistics presented in any given summary module. As mentioned above, this may be less than the number of subjects in the analysis population.
 - In the quantitative modules describing continuous variables (and thus presenting sample size, means, and standard deviations), the sample size should be the number of non-missing observations.
 - For categorical variables that are presented in frequency tables, the module should present the total count in addition to the count in each category. Percentages should be calculated using this total as the denominator, and the percentage corresponding to the sum itself (that is, 100%) should be presented to indicate clearly to a reviewer the method of calculation. Missing data will not contribute to the calculation of percentages.
- Sorting: Listings will be sorted by treatment group, subject identification number and date, if applicable. If a listing is sorted in a different manner, a footnote will indicate as such.
- General formatting rules: Rounding for all variables will occur only as the last step, immediately prior to presentation in listings, tables, and figures. No intermediate rounding will be performed on derived variables. The standard rounding practice of rounding numbers ending in 0-4 down and numbers ending in 5-9 up will be employed.
- The presentation of numerical values will adhere to the following guidelines:
 - Raw measurements will be reported to the number of significant digits as captured electronically on the eCRFs.
 - Standard deviations will be reported to one decimal place beyond the number of decimal places the original parameter is presented.
 - Means will be reported to the same number of significant digits as the parameter, unless the parameter is an integer, then 1 decimal place will be reported.
 - Calculated percentages will be reported with no decimals.

Version 1

- Dates will be formatted as DDMMMYYYY. Partial dates will be presented on data listings as recorded on CRFs.
- Time will be presented according to the 24-hour clock (HHMM).

8. TABLES, LISTINGS AND FIGURES

Tables

- 1. Summary of Subject Enrollment and Disposition.
- 2. Summary of Subject Demographics at Screening (mITT population).
- 3. Summary of Subject Demographics at Screening (PP Population).
- 4. Summary of Medical History/Other Concomitant Illness at Screening.
- 5. Summary of Physical Exam Abnormalities.
- 6. The Difference in proportion of patients that are identified as cured on Study Day 15 (Visit 5) Treated with Ivermectin and Sklice (mITT population).
- 7. The Difference in proportion of patients that are identified as cured on Study Day 15 (Visit 5) Treated with Ivermectin and Sklice visit (PP population).
- 8. The Difference in proportion of patients that are identified as cured on Study Day 15 (Visit 5) Treated with Ivermectin Vs Placebo and Sklice Vs Placebo (mITT population).
- 9. The Difference in proportion of patients that are identified as cured on Study Day 15 (Visit 5) Treated with Ivermectin Vs Placebo and Sklice Vs Placebo (PP population).
- 10. Summary of Head Lice visual examination at each visit (mITT population).
- 11. Summary of Head Lice visual examination at each visit (PP Population).
- 12. The Difference in proportion of patients that are identified as cured on Study Day 2 (Visit 3) Treated with Ivermectin and Sklice (mITT population).
- 13. The Difference in proportion of patients that are identified as cured on Study Day 2 (Visit 3) Treated with Ivermectin and Sklice (PP population).
- 14. The Difference in proportion of patients that are identified as cured on Study Day 2 (Visit 3) Treated with Ivermectin Vs Placebo and Sklice Vs Placebo (mITT population).
- 15. The Difference in proportion of patients that are identified as cured on Study Day 2 (Visit 3) Treated with Ivermectin Vs Placebo and Sklice Vs Placebo (PP population).
- 16. Summary of self-assessment of itching and stinging/ burning sensations at each visit (mITT population).
- 17. Summary of self-assessment of itching and stinging/ burning sensations at each visit (PP population).
- 18. Summary of change of self-assessment of itching and stinging/ burning sensations from baseline at each visit (mITT population).
- 19. Summary of change of self-assessment of itching and stinging/ burning sensations from baseline at each visit (PP population).
- 20. Summary of local skin/scalp irritation assessment at each visit (mITT population).
- 21. Summary of local skin/scalp irritation assessment at each visit (PP population).
- 22. Summary of ocular irritation assessment at each visit (mITT population).
- 23. Summary of ocular irritation assessment at each visit (PP population).
- 24. Summary of change of local skin/scalp irritation assessment from baseline at each visit (mITT population).
- 25. Summary of change of local skin/scalp irritation assessment from baseline at each visit (PP population).
- 26. Adverse Events by System Organ Class and Preferred Term.
- 27. Adverse Events with incidence >5 % by System Organ Class and Preferred Term.

- 28. Treatment Emergent Adverse Events by System Organ Class and Preferred Term.
- 29. Treatment Emergent Adverse Events by maximum Severity.
- 30. Summary of Treatment Emergent Adverse Events possible or probably related to the study drug.
- 31. Summary of Serious Adverse Events by System Organ Class and Preferred Term.
- 32. Summary of Concomitant Medications.

Data Listings

- 1. Listing of Analysis Population and Study Completion.
- 2. Listing of Subjects Who Discontinued.
- 3. Listing of Patients Excluded from Per Protocol Efficacy Analysis.
- 4. Listing of Protocol Deviation.
- 5. Listing of Subject Demographics.
- 6. Listing of Drug Accountability.
- 7. Listing of Head Lice visual examination of index subjects.
- 8. Listing of Head Lice visual examination of house hold members.
- 9. Listing of Subject Diary data.
- 10. Listing of Patient Self-assessment.
- 11. Listing of local skin/scalp irritation assessment.
- 12. Listing of ocular irritation assessment.
- 13. Listing of Adverse Events.
- 14. Listing of Treatment Emergent Adverse Events.
- 15. Listing of Non-Treatment Emergent Adverse Events.
- 16. Listing of Adverse drug reaction.
- 17. Listing of Treatment Emergent Adverse Events which lead to discontinuation of study treatment.
- 18. Listing of Non-Treatment Emergent Adverse Events which lead to discontinuation of study treatment.
- 19. Listing of Treatment Emergent Adverse Events which lead to Withdrawal from the study.
- 20. Listing of Non-Treatment Emergent Adverse Events which lead to Withdrawal from the study.
- 21. Listing of Concomitant Medication.
- 22. Listing of Serious Adverse Events.
- 23. Listing of Serious Adverse Events with fatal outcome.
- 24. Listing of Medical History.
- 25. Listing of Physical Examination.
- 26. Listing of Pregnancy test.
- 27. Listing of Subject Vital Signs for Randomized Population.
- 28. Listing of Inclusion/Exclusion Criteria (Randomized Population).

Figures

- 1. The proportion of patients that are identified as cured at the Study Day 2 and 15. (mITT population).
- 2. The proportion of patients that are identified as cured at the Study Day 2 and 15. (PP population).
- 3. The summary of self-assessment of itching. (mITT population).
- 4. The summary of self-assessment of itching. (PP population).
- 5. The summary of self-assessment of stinging/burning sensations at each visit. (mITT population).
- 6. The summary of self-assessment of stinging/burning sensations at each visit. (PP population).
- 7. The summary of local skin/scalp irritation assessment each visit. (mITT population).
- 8. The summary of local skin/scalp irritation assessment at each visit. (PP population).
- 9. The summary of ocular irritation assessment each visit. (mITT population).
- 10. The summary of ocular irritation assessment at each visit. (PP population).

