8.2.2 Relationship to Study Drug

The Investigator will use the following definitions to assess the relationship of the AE/SAE to the use of investigational product:

Definitely Related The event occurred within a reasonable time after drug administration or drug

concentration and body fluids demonstrated that the study drug was present: the event could not be reasonably explained by known characteristics including concomitant

therapies; the adverse event abated after discontinuing the study drug.

Probably Related The event has a strong temporal relationship to study drug or recurs on re-challenge and

another etiology is unlikely or significantly less likely.

Possibly Related The event has a strong temporal relationship to the study drug and an alternative etiology

is equally or less likely compared to the potential relationship to study drug.

Probably Not Related The event has little or no temporal relationship to the study drug and/or a more likely

alternative etiology exists.

Not Related The event is due to an underlying or concurrent illness or effect of another drug and is not

related to the study drug (e.g., has no temporal relationship to study drug or has a much

more likely alternative etiology).

If an Investigator's opinion of not related to study drug is given, an alternate etiology must be provided by the Investigator for the AE.

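### The title of SAP Table 30 covers only possibly or probably related TEAEs, which conflicts with the promised summary of all drug-related TEAEs and leaves out the protocol's strongest category, Definitely Related.

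*SAP*

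**What the plan says.** SAP section 8 lists Table 30 as "Summary of Treatment Emergent Adverse Events possible or probably related to the study drug". It is a title only, with no shell, selection rule or footnote. No other table in the list is organised by relationship to study drug.

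The methods text is wider. SAP 5.4, SAP 5.4.1 and Protocol 10.4.3 each call for a separate summary of TEAEs related to study drug and do not limit it to certain grades. The same sections contain two rules on relationship:

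- Missing values: "Should an event have a missing severity or relationship, it will be classified as having the highest severity and/or strongest relationship to study drug".
- Several events in one subject under one preferred term: the term takes the strongest relationship that the investigator assigned.

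The grades come from Protocol 8.2.2, whose top level opens "Definitely Related The event occurred within a reasonable time after drug administration". The SAP neither repeats the scale nor defines what counts as related.

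**The concern.** A table of drug-related events should include the events that the investigator is surest about. This title stops one grade short of the top of the scale. The two handling rules make it worse, because both move events upwards. Imputing a missing relationship to the strongest grade is meant to be conservative: a doubtful event counts as related. With a table limited to the two lower positive grades, the same rule would take the event out of the related-event count.

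What is at stake is descriptive safety reporting. Comparing the safety and local tolerability of the test lotion with the reference is the secondary objective. Safety data are summarised without formal testing, so the tables are themselves the safety result. Table 30 is the only one that would show TEAEs attributed to treatment, by arm. Two programmers, one following the title and the other the methods text, could produce different counts from the same data.

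**Working it through.** No sample size, power or error rate enters this point, and the plan gives no figure to reproduce. The check sets the texts side by side.

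**Step 1: map the protocol scale (Protocol 8.2.2) onto the Table 30 title (SAP section 8).**

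| Level | Opening of the protocol definition | Positive? | Named in the title? |
|---|---|---|---|
| 1 | "Definitely Related The event occurred within a reasonable time after drug administration" | Yes | No |
| 2 | "Probably Related The event has a strong temporal relationship to study drug or recurs on re-challenge" | Yes | Yes |
| 3 | "Possibly Related The event has a strong temporal relationship to the study drug" | Yes | Yes |
| 4 | "Probably Not Related The event has little or no temporal relationship to the study drug" | No | No |
| 5 | "Not Related The event is due to an underlying or concurrent illness or effect of another drug" | No | No |

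There are 3 positive levels and the title names 2, so 3 − 2 = 1 is left out, and it is the strongest.

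**Step 2: apply the missing-relationship rule (SAP 5.4 and 5.4.1, Protocol 10.4.3).** Such an event is "classified as having the highest severity and/or strongest relationship to study drug". On the protocol scale the strongest relationship is level 1. Level 1 is outside the title, so every TEAE with missing causality falls outside it too.

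**Step 3: apply the multiple-event rule (same sections).** Take a subject with one possibly related and one definitely related event under the same preferred term. The term is assigned level 1. Read literally, that subject then leaves Table 30 for that term, although the possibly related event alone would have qualified.

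**Step 4: compare with the promised summary.** The methods text promises all TEAEs related to study drug. Levels 1 to 3 all meet that description. A table built to the title therefore falls short by level 1 and by everything that steps 2 and 3 move into it.

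**Step 5: find where the omitted events would still appear.** TEAEs of any causality are in Table 26 (all adverse events), Table 28 (TEAEs by system organ class and preferred term), Table 29 (TEAEs by maximum severity) and Listings 13 and 14. Listing 16, on adverse drug reactions, may also show them, but its selection criterion is not stated. None of these tables is a summary by relationship.

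**Step 6: bound the size.** If no TEAE is graded definite and none has missing causality, the title and the methods text give the same counts. If every related TEAE is definite or imputed, a table built to the title is empty. The omitted share of related events can therefore lie anywhere from 0% to 100%. Protocol 2.3.1 mentions reactions seen in less than 1% of treated subjects but does not split them by causality grade, so it does not narrow the range.

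**The case against.** The strongest reply is that a table title is not a programming specification. The methods text is correct and also carries the imputation rule, so a programmer working from SAP 5.4.1 would include definite events. The title may be loose shorthand for at least possibly related. Causality wording is loose elsewhere as well: Protocol 8.1 uses a related / probably related split that does not match the five levels. This stands in part. A reader might infer that the sponsor has decided to drop definite events. The documents do not show such a decision; they show a conflict between a title and the methods text. The conflict still needs resolving, because the table list is the only place where this output is itemised and nothing in the SAP says which text prevails.

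The second reply is that no event disappears from the safety report. That stands, for the reason in step 5. What would be incomplete is the by-relationship summary. The local-tolerability part of the secondary objective is also covered separately, by Tables 16 to 25, whatever the causality.

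The third reply is that few events may be affected. Protocol 8.1 requires the investigator to record a relationship for each adverse event, so missing values may be rare. That is fair and cannot be settled from the documents.

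A reader might also infer that local reactions soon after application would mostly be graded Definitely Related, so that the table would lose the commonest events. The documents do not support this. The definition also requires that the event have no other reasonable explanation and that it subside once the drug is stopped. A single 10-minute application leaves no continuing treatment to stop, and exclusion criterion 4 recognises that scalp findings may be due to the infestation itself. Probably or Possibly Related could fit just as well.

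**Conclusion.** The point holds as an internal inconsistency in the specification of one safety table. The title of Table 30 conflicts with SAP 5.4 and 5.4.1, with Protocol 10.4.3 and with the scale in Protocol 8.2.2. The consequence is conditional: if the table is built to its title, the only by-relationship summary omits definitely related TEAEs, TEAEs with imputed causality, and preferred terms raised to definite.

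The size is one of three positive categories. No event count can be attached, and any split of events by grade would be invented. The conclusion assumes that the protocol's five-level scale is the one used on the case report form and that the strongest relationship means Definitely Related. Both follow from the protocol, although the SAP states neither.

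The superiority tests, the bioequivalence interval and the sample size do not depend on this table. It is a reporting correction that should be made before unblinding, so that the choice between title and methods text is not made with the results in view.

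**What to change.** Retitle Table 30 as *TEAEs definitely, probably or possibly related to study drug, including events with missing relationship imputed to the strongest category*. In SAP 5.4.1, define a related TEAE once in the same terms, with a reference to the scale in Protocol 8.2.2.

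The cost is one title line and one sentence of definition. No new data, visits or analyses are needed. The only downside is that the reported related-event counts may be somewhat higher than under the present title.

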APPENDIX A: ITCHING SENSATION SCALE

Score	Grade	Definition
0	None	The scalp does not itch.
1	Mild	Occasional episodes of itching, not bothersome.
2	Moderate	Frequent, several times a day, bothersome.
3	Severe	Nearly constant, frequent, very bothersome.

Itching - Intense, distracting irritation or tickling sensation in the last 24 hours

